The primary goal is to characterize neurobiological processing of and behavioral responding in cue reactivity, reward processing, executive control, and intrinsic network connectivity differences between HC and CD participants at baseline, during and following iTBS intervention. The Expanded Feasibility Study is powered to assess neuroplastic changes between completers in the CD group who receives active iTBS (N = 30), the CD group who receives sham iTBS (N = 30), and the HC group who receives a within-participant active/sham iTBS manipulation (N = 40). Specifically, we will test for potential neural plasticity over time in the CD cohort and relate any changes to treatment group ongoing substance use (i.e., reductions or maintenance of use). Each CD participant is expected to complete a total of 8 MRI scan sessions across 5 days over a 14-week period 1. Multiple MRI scan sessions will allow for direct comparisons of neural plasticity within participants over time.

C. Aims

1. To characterize neural differences between CD and HC participants at baseline.
2. To determine if iTBS alters networks related to cognitive/affective function by:
 - a. Identifying networks and cognitive/affective functions that change with acute treatment in both HC and CD.
 - b. Identifying networks and cognitive/affective functions that show sustained change (2 weeks after end of treatment) with chronic treatment in CD.
3. To determine if imaging measures can reliably predict which individuals will respond to treatment, either at baseline or after completion of treatment.
4. To determine the trajectory of neural plasticity related to chronic iTBS and cocaine abstinence.
5. To monitor safety of iTBS applied in cocaine dependent individuals.

D. Hypotheses

1. Functional imaging correlates of cue reactivity, reward processing, executive control, and intrinsic network connectivity will differentiate CD and HC participants at baseline.
2. Within the CD group, measures of cue reactivity, reward processing, executive control, and intrinsic network connectivity will be predictive of treatment success and reduction in drug use.
3. Acute iTBS will alter cue reactivity, reward processing, executive control, and intrinsic network connectivity in both CD and HC.

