General fMRI power. Since fMRI is the main outcome measurement utilized in the present protocol, the key power analysis pertains to the fMRI data. However, prospective power analyses for fMRI data are complicated for several reasons. First, fMRI data are analyzed in a hierachal manner such that both the *intra*-participant variance from the time-course data and the *inter*-participant variance across individuals could affect statistical power. A large number of time points tend to mitigate effects of intra-participant variance, but temporal autocorrelation and scanner limitations limit the number of independent measurements per unit time and thus the number of independent time points that are collected. In addition, effect sizes and both types of variance will vary spatially. Because of this, a given study may have sufficient power to detect differences in some brain regions, but lack sufficient power in other regions where the null hypothesis is false. Finally, fMRI analysis consists of a very large number of non-independent multiple comparisons, greater than 1.5 million at the group level, necessitating correction methods less severe than a Bonferroni correction, as discussed above. Thus, a proper power analysis on fMRI data requires simulating all of these effects. Desmond and Glover¹⁶⁴ have performed such a simulation. They show for a relatively modest signal change of 0.5% during a cognitive task and with an intra-participant standard deviation of 0.75% and an inter-participant standard deviation of 0.5%, that 11 participants are required for a power of 0.8 using $p < 0.05$. Using a false positive rate of $p < 0.002$, a level more consistent with a cluster size threshold to correct for multiple comparisons¹⁶⁵, and with the variances kept the same, approximately 21 participants are needed for an expected signal change of 0.5% and 11 participants for a signal change of 0.75%. For more than ~100 independent time points, power (and hence the intra-participant variance) is relatively independent of the number of time points¹⁶⁴. All current analyses should fall within this range.

There are no published reports of the effects of chronic application of iTBS in cocaine users with functional connectivity measures on which to base a power analysis and the acute effects of iTBS on functional connectivity alterations are not relevant to our study as we seek to understand neural changes after *chronic* application of iTBS.

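### The general fMRI power figures (11 and 21) behave as one-group sample sizes and are not labelled so; on the same inputs, an active-versus-sham task contrast of 0.5% at p < 0.002 needs about 34–37 per arm two-sided, against 30 planned

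*Combined protocol and SAP*

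**What the plan says.** Section III.G.vi, in the paragraph on general fMRI power, opens: "Since fMRI is the main outcome measurement utilized in the present protocol, the key power analysis pertains to the fMRI data". It then cites a published simulation. "They show for a relatively modest signal change of 0.5% during a cognitive task", with "an intra-participant standard deviation of 0.75% and an inter-participant standard deviation of 0.5" per cent, "11 participants are required for a power of 0.8 using" p < 0.05. At p < 0.002, which the paragraph regards as closer to a cluster-size correction, "approximately 21 participants are needed for an expected signal change of 0.5% and 11 participants for a signal change of 0.75" per cent. On within-participant noise it adds: "For more than ~100 independent time points, power (and hence the intra-participant variance) is relatively independent of the number of time points". The paragraph does not state sidedness, and does not say whether the numbers are for one group or for each of two.

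The following paragraphs of III.G.vi size a different quantity: post-treatment functional connectivity, active versus sham, with means 0.405 and 0.210, SD 0.299, effect size 0.65, a one-tailed test at .05 and power 0.8, giving 30 per group.

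Section III.B (Goals) says: "The Expanded Feasibility Study is powered to assess neuroplastic changes between completers in the CD group who receives active iTBS (N = 30") and the 30 who receive sham. It does not limit this to connectivity. Sections III.E and III.F.i tie the 30 completers per arm to a power analysis for MRI measures in general. Hypotheses 4 and 5 in III.D compare chronic active with sham iTBS on cue reactivity, reward processing and executive control as well as intrinsic connectivity.

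**The concern.** Three of the four constructs in the active-versus-sham hypotheses are measured by task fMRI, and for these the plan's only power basis is the general paragraph. A sample size for detecting an activation in one group cannot be carried over to a difference between two independent arms. With the same effect and SD, the variance of the estimated difference doubles, so each arm needs nearly twice as many participants. Because the paragraph is silent on this, its 21 can be read as a per-arm requirement that 30 completers exceed.

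What is at stake is how a null task-fMRI result would be read. A reader relying on III.B would take an absence of active-versus-sham difference at the corrected threshold as coming from an adequately powered comparison.

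**Working it through.** **Inputs** (III.G.vi, general fMRI power paragraph): signal change 0.5% or 0.75%; inter-participant SD 0.5%; intra-participant SD 0.75%; power 0.8; p < 0.05 or p < 0.002. Planned completers are 30 per CD arm (III.B).

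**Assumption.** The plan gives neither the noise model nor the exact number of time points. I let the intra-participant term add k × 0.75²/100 to the variance, with k = 0, 1, 2 or 4:

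SD = √(0.5² + k × 0.75²/100), d = signal / SD.

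- k = 0: SD = 0.500, d = 1.00 for 0.5% and 1.50 for 0.75%.
- k = 4: SD = √(0.25 + 0.0225) = 0.522, d = 0.96 and 1.44.

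**Step 1: reproduce the plan's figures.** One-sample t-test, exact power from the noncentral t with noncentrality d√n and n − 1 degrees of freedom.

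| Case | Plan | One group, two-sided | One group, one-sided |
|---|---|---|---|
| 0.5%, p < 0.05 | 11 | 10–11 | 8–9 |
| 0.5%, p < 0.002 | 21 | 21–22 | 19–20 |
| 0.75%, p < 0.002 | 11 | 12–13 | 11 |

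The two-sided one-group test comes within two participants of all three figures and fits both 0.5% cases. The one-sided test fits only the 0.75% case. Adding the full intra-participant SD without averaging (SD = √(0.25 + 0.5625) = 0.901, d = 0.555) gives 28 and 56 two-sided for the 0.5% cases, so that model is not the one behind the figures.

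**Step 2: the same inputs with two arms.** Two-sample t-test, 1:1, noncentrality d√(n/2) with 2n − 2 degrees of freedom. Here the stated signal is treated as the between-arm difference, with the same SD in each arm.

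| Case | Per arm, two-sided | Per arm, one-sided | Power at 30 per arm, two-sided |
|---|---|---|---|
| 0.5%, p < 0.05 | 17–19 | 14–15 | 95–97% |
| 0.5%, p < 0.002 | 34–37 | 30–33 | 68–73% |
| 0.75%, p < 0.002 | 17–18 | 15–16 | about 99% |

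For 0.5% at p < 0.002, one-sided power at 30 per arm is 76–80%. If 21 were read as a per-arm number, two-sided power would be 43–48%. None of the plan's three figures matches the two-arm column, which also points to a one-group origin.

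**Step 3: sensitivity to the difference.** A 0.5% task signal is a whole activation; a treatment difference between arms could be smaller. With k = 2 (SD = 0.511), two-sided p < 0.002 and 30 per arm, a difference of 0.4% (illustrative) has about 43% power and one of 0.25% (illustrative) about 10%.

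**Step 4: the connectivity calculation.** d = (0.405 − 0.210)/0.299 = 0.195/0.299 = 0.65. A one-tailed two-sample t-test at .05 gives 30 per group with power 0.803, as the plan states.

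**The case against.** Much of the opposing case stands. The general paragraph reports a published simulation and does not itself claim to size the active-versus-sham contrast. It also warns that power can be sufficient in some brain regions and lacking in others. Nothing in it is miscalculated. The shortfall appears in one of its three scenarios, and it depends on sidedness that the paragraph leaves unstated: one-sided, and with no within-participant noise at all (k = 0), 30 per arm just reaches 80%. The only sidedness stated in a power calculation in the plan is the one-tailed connectivity test. Treating 0.5% as a between-arm difference with the same SD is also a borrowing, because the plan gives neither quantity for task fMRI, and its paired and factorial analyses would have other variances.

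These points narrow the finding but do not remove it. One-sided testing misses both 0.5% figures, so two-sided is the better reading of the case at issue. The general caution about regions does not tell a reader that the numbers are one-group. And if the borrowed effect is not accepted, the task contrasts have no sample-size basis at all, while III.B still calls the comparison powered.

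Two stronger readings are tempting. A reader might infer that the trial's 30 per arm rests on a one-group calculation. It does not: it comes from the two-group connectivity calculation, which reproduces. A reader might also infer that every figure in the paragraph falls short once two arms are compared. Only the 21 case does.

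**Conclusion.** The concern holds as a matter of labelling and scope. The figures 11 and 21 reproduce as one-group activation sizes, are not identified as such, and are the only power basis for task fMRI, although the plan describes 30 versus 30 as powered for MRI measures. At the plan's own stricter threshold, a 0.5% between-arm difference needs about 34–37 per arm two-sided (30–33 one-sided), and 30 per arm gives about 68–73% power (76–80% one-sided).

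This rests on three assumptions: a between-arm difference of the full 0.5%, the same SD as in the one-group case, and within-participant noise averaged over about 100 time points. The one-group origin is inferred from the match with the stated inputs; the cited simulation was not available to confirm it.

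**What to change.** In the general fMRI power paragraph of III.G.vi, confirm against the cited simulation that 11 and 21 are one-group figures and label them so. Add the two-arm equivalents (17–19, 34–37 and 17–18 per arm, two-sided) and the power at 30 per arm. State sidedness, and say that the between-arm difference and SD are carried over from the one-group case as an illustration.

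In III.B, and where III.E and III.F.i refer to power for MRI measures, limit the claim for CD active versus sham to the connectivity contrast. Add that task-activation contrasts at the p < 0.002 threshold have less than 80% power, two-sided, for a 0.5% difference.

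No participants are added and no design or analysis changes. The cost is a less favourable stated figure.

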4. Within the CD group, chronic Active iTBS, relative to Sham, will modulate cue reactivity, reward processing, executive control, and intrinsic network connectivity, which will relate to changes in drug use after the 2-week treatment.
5. Within the CD group, chronic Active iTBS, relative to Sham, will modulate cue reactivity, reward processing, executive control, and intrinsic network connectivity such that neuronal processing in CD participants following iTBS will approximate that in HC (i.e. normalize processes).

E. Experimental Design

Two groups of participants will be recruited: 1) treatment seeking cocaine dependent individuals (CD; n = 90; 45 Active-iTBS and 45 Sham-iTBS); 2) matched community healthy controls (HC; n = 45; within-subject crossover iTBS manipulation). Fifty CD participants in each group will be recruited to obtain the necessary number of participants (n = 30) to complete treatment (see power analysis calculated to ensure necessary power for MRI measures). CD participants may stay in the on-campus inpatient facility approved by the NIDA Clinical Director's office while they participate in this iTBS protocol. The inpatient unit will be available to every CD participant to increase compliance with protocol scheduling. In general, participants will arrive at the inpatient facility the day before their iTBS session. CD participants will be escorted by study staff to and from the inpatient unit on treatment days, which may include automotive pick-up service (e.g., shuttle, taxi). **We will implement a within-subject crossover Active-**

and Sham-iTBS method with the HC participants to provide for the necessary sham control.

[figure not shown]
All participants will receive a post-iTBS nursing assessment and cognitive assessment prior to discharge. An approximate timeline is described below but may vary to account for participant, staff, and facility availability. **All participants, regardless of group, will be scheduled to complete baseline data collection (Characterization; Figures 1 & 2: Visit 1).** An initial scan (Scan 1) will be performed to acquire MRI localization to be used in the iTBS protocol as well as cognitive and affective characterization imaging tasks (week 1); Visit 2 clinical characterization instruments (per protocol 10-DA-N457) and MRI scan (Scan 2; week 1) [participants may be scheduled to complete these characterizations over more than one day, if needed to ensure completion prior to the first iTBS day];

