1	4	1	5	5
1	4	2	10	15
1	4	3	10	25
2	5	4	20	45
2	5	5	20	65
2	5	6	20	85
3	6	7	20	105
3	6	8	20	125
3	6	9	20	145
4	7	10	30	175

4	7	11	30	205
4	7	12	30	235
5	8	13	40	275
5	8	14	40	315
5	8	15	40	355
6	9	16	40	395
6	9	17	40	435
6	9	18	40	475
7	10	19	40	515
7	10	20	40	555
8	11	21	40	595
8	11	22	60	655
9	12	23	60	715
9	12	24	60	775
10	13	25	60	835
10	13	26	80	915
11	14	27	80	995
11	14	28	80	1,075.00

Introduction to Treatment: Before initiation of iTBS, a session will take place to assess and attempt to enhance individual motivation and preparation to reduce or eliminate cocaine use. During this session, participants may repeat some assessments, such as the BCCMA. This session is designed to inform the participant of the treatment trajectory, introduce the concept of CM, introduce techniques to manage cue-induced craving, and assess and enhance their motivation to quit using cocaine. This will be conducted by the MAI, study therapist, or designee.

F. Inclusion and Exclusion

i. Description of the Study Population

We will enroll 45 (within-subject crossover active- vs sham-iTBS manipulation) HC and 90 treatment seeking CD (45 active-iTBS and 45 sham-iTBS) individuals who meet the inclusion and exclusion criteria. Fifty CD participants in each group will be recruited

to obtain the necessary number of (n = 30) treatment completers (see power analysis; calculated to ensure necessary power for MRI measures). Screening will be conducted under the approved NIDA IRP general screening protocol to determine eligibility (Expanded Feasibility Study Eligibility Checklist; Appendix 31). Participants will also be required to enroll in the NIDA protocol 10-DA-N457 to gather characterization data not otherwise collected in this protocol but which will be used in the planned analyses. Generally, CD participants will be current cocaine users and HC participants will be non-users matched on measures including age, sex, ethnicity, race, etc.

ii. Inclusion Criteria

1. Be able to give valid informed consent.
2. Agree to also participate in study 10DAN457, where characterization information is gathered and shared with this protocol.
3. Be 22 – 60 years of age.
 - a. Justification: Many neural processes change with age, and these changes could introduce unwanted variability in both behavioral and MRI signals.
 - b. Screening tool: Self-report.
4. Right-handed.
 - a. Justification: Differences in hemispheric dominance could confound iTBS administration and MRI measurements.

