Nonetheless, there is a single published report in a sample of participants with major depression where functional connectivity was measured pre- and post-rTMS treatment¹⁶⁶. In this report, the mean functional connectivity pre-TMS (0.38 z-scored connectivity) was greater than post-TMS (0.22 z-scored connectivity) with an average standard deviation of 0.17 z-scored connectivity. We calculated the effect size to be 0.91. This effect size is likely unrealistically high due to 'double-dipping' in their analyses¹⁶⁷, a small sample size, and publication bias toward significant effects, all of which affect the effect size calculation and generalizability.

To better assess a more realistic effect size based on these findings, we simulated an effect size (N =10,000) based on the published means and standard deviations. The effect size that falls 1 standard deviation below the mean was 0.64. This effect is remarkably close to a published report comparing functional connectivity between healthy controls and cocaine users⁴⁴ without a TMS intervention (calculated effect size of 0.67).

Together, when assessing functional connectivity differences post-iTBS treatment between active and sham groups, we conservatively select an effect size 0.65 to capture a reliable effect while reducing the likelihood of committing a Type II error and a power level (1- β) of 0.8 to achieve an appropriate balance between the ability to detect significant differences and the number of participants needed. Therefore, for power analysis calculations (i.e., Statistical Analysis Plan), we anticipate a mean functional connectivity measure post-iTBS for the sham group to be 0.210 z-scored connectivity and active group to be 0.405 z-scored connectivity with a standard deviation of 0.299 z-scored connectivity, which produces an effect size of 0.65 and an estimated sample size needed per group to be 30 with a one-tailed *t*-test assuming a *p*-value of .05. We anticipate approximately 60% retention rate by visit 19, based on previous NIDA protocols. Therefore, 100 CD participants will be recruited at baseline, 45 active and 45 sham iTBS, to acquire the necessary 30 participants in each group for analysis.

IV. COLLECTION AND STORAGE OF HUMAN SPECIMENS OR DATA

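### The plan needs 30 completers per arm, but 45 per arm at its own 60% retention gives 27, and the sample-size text totals 45 + 45 as 100

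*Combined protocol and SAP*

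**What the plan says.** Section III.G.vi (Statistical Analysis) sizes the active-versus-sham comparison on post-treatment functional connectivity. The authors write that "we conservatively select an effect size 0.65", together with "a power level (1- β) of 0.8". From assumed means of 0.210 (sham) and 0.405 (active) and a standard deviation of 0.299 they obtain "an estimated sample size needed per group to be 30 with a one-tailed" t-test, "assuming a *p*-value of .05".

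The next step allows for dropout: "We anticipate approximately 60% retention rate by visit 19, based on previous NIDA protocols". From this the plan concludes that "100 CD participants will be recruited at baseline, 45 active and 45 sham iTBS, to acquire the necessary 30 participants in each group".

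Other sections give the CD enrolment as follows:

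- **Précis (study population):** 90 CD, 45 per arm, with 45 healthy controls (HC).
- **III.E (Experimental Design):** 90 CD as 45 + 45, followed at once by "Fifty CD participants in each group will be recruited to obtain the necessary number of participants (n = 30) to complete treatment".
- **III.F.i (Description of the Study Population):** 45 "HC and 90 treatment seeking CD (45 active-iTBS and 45 sham-iTBS) individuals", followed by the same statement that fifty per group will be recruited.
- **III.B (Goals):** the study is powered on completers numbering 30 active, 30 sham and 40 HC.
- **IV.E (enrollment tables):** a ceiling of 135 and 100 completers required.

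**The concern.** The recruitment figure is presented as following from the 30 per group and the 60% retention, and it does not follow. One sentence also gives a total that its own two parts contradict. Because both 45 and 50 per arm appear in the current text of three sections, this cannot be put down to a single typing slip.

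Two things are at stake. First, the 80% power claim depends on 30 analysable participants per arm. If the trial enrols 45 per arm and retention is as forecast, it will not have them. Second, enrolled sample size is a basic design parameter. With two values in force, staff and the oversight bodies cannot tell when enrolment is complete or whether a shortfall has occurred.

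**Working it through.** **Inputs.** All from III.G.vi unless noted: means 0.210 and 0.405, SD 0.299, effect size 0.65, one-tailed alpha 0.05, power 0.80, retention about 60% by visit 19, 45 per arm. Ceiling 135 and 100 completers from IV.E; 45 HC from the Précis and III.E; 30 + 30 + 40 completers from III.B.

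**1. Reproduce the 30 per group.** Effect size d = (0.405 − 0.210) / 0.299 = 0.195 / 0.299 = 0.652, which the plan rounds to 0.65. For a two-sample t-test with n per arm, power comes from the noncentral t distribution with 2n − 2 degrees of freedom and noncentrality d × √(n/2). At n = 30 and d = 0.65 the noncentrality is 0.65 × √15 = 2.52 on 58 degrees of freedom, and one-tailed power is 0.800 (0.803 at d = 0.652). The 30 per group is therefore correct for the test as specified.

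**2. Inflate for dropout.** Enrolment per arm = 30 / 0.60 = 50, or 100 in total. The stated 45 per arm is 5 short. It would be right only at a retention of 30 / 45 = 66.7%.

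**3. Which target is operative.** 135 − 45 HC = 90 CD, which agrees with the Précis. Recruiting 50 per arm with 45 HC would need 145, which exceeds the ceiling. So the version that satisfies the power calculation cannot be enrolled under the document's own table.

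**4. Yield and power at 45 per arm.** 45 × 0.60 = 27 per arm, 54 in total. At n = 27 the noncentrality is 0.65 × √13.5 = 2.39 on 52 degrees of freedom, and one-tailed power is 0.762 (0.764 at d = 0.652). The loss is 0.800 − 0.762 = 0.038.

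**5. Sensitivity of the yield to retention.**

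| Retention | Completers from 45 | Enrolment needed for 30 |
|---|---|---|
| 55% | 24.8 | 54.5 |
| 60% | 27.0 | 50.0 |
| 65% | 29.3 | 46.2 |
| 66.7% | 30.0 | 45.0 |
| 70% | 31.5 | 42.9 |

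**6. Chance of reaching the target.** This assumes, as the plan does not, that participants are retained independently with probability exactly 0.60.

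| | 45 per arm | 50 per arm |
|---|---|---|
| One arm reaches 30 | 0.22 | 0.56 |
| Both arms reach 30 | 0.05 | 0.31 |
| 60 completers in total | 0.12 | 0.54 |

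**7. Sidedness, for context.** Two-sided power is 0.650 at 27 per arm and 0.697 at 30 per arm. Most of the gap between 65% and 80% therefore comes from the choice of a one-tailed test, not from the recruitment error.

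**The case against.** The best defence is that the documents also contain figures that work: 50 per arm and 100 in total deliver exactly 30 completers at 60%. On that view the fault is an unreconciled pair of targets, and the power shortfall arises only if 45 is the one in use. That is fair as logic. But the Précis, the group sizes in III.E, III.F.i and III.G.vi, and the 135 ceiling all use 45 per arm or 90, so the conditional is very likely met. If 50 is what is meant, all of those places are wrong and still need correcting.

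A second point is that the effect is small. Retention is given only approximately, and at 65% the yield is about 29 per arm with power of 0.79. This stands as a comment on size. It does not make 45 follow from 60%.

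Third, the completer counts in III.B and IV.E imply 60 of 90 CD participants, which is 66.7%. That figure is a requirement, not a forecast, and it conflicts with the only retention rate the plan forecasts.

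Fourth, III.G.vi allows participants with at least five treatment days to be analysed. That option applies if most participants fail to complete ten days, and it adds nobody if the 60% already counts everyone retained to visit 19. The completer definition in III.G.i is in fact stricter, requiring ten treatment days within three weeks as well as visit 19.

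Finally, the probabilities of hitting the target look poor for any plan sized on expected completers, as the 50-per-arm column shows. Power also does not depend on both arms reaching 30. Those probabilities are supporting detail only.

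**Conclusion.** The concern holds. The 30 per group is right for the stated one-tailed test; the error is in the recruitment step. At the plan's own 60% retention, the working target of 45 per arm gives 27 completers per arm, 3 short in each. Power is then about 76% instead of 80% for an effect size of 0.65. Separately, the text gives 90 and 100 for the same total, and the larger figure does not fit under the enrollment ceiling.

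This rests on 45 per arm being operative and on the planning values for effect size, standard deviation and retention. The power loss is modest. The correction is nevertheless needed, because the stated power and the enrolled sample size cannot both be true as written.

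**What to change.** Choose one target and use it in the Précis, III.B, III.E, III.F.i, III.G.vi and IV.E.

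- **Keep 90 CD (45 per arm).** Remove the references to 100 CD and to fifty per group. State 27 expected completers per arm at 60% retention and power of about 76% (one-tailed, effect size 0.65; 65% if a two-sided figure is also reported). Change the completer counts in III.B and IV.E to match: 27 + 27 + 40 = 94 in place of 100. Alternatively, keep 30 per arm and justify retention of at least 67%. Either way the cost is wording only, with no extra participants. Stating 27 makes the quoted power slightly less favourable.
- **Adopt 100 CD (50 per arm).** Correct the 45 + 45 and 90 entries and raise the ceiling from 135 to 145. This keeps the 80% claim at the cost of ten more CD participants.

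In the same edit, check the figure of about 170 participants in IV.B (Human Data Sharing). It matches neither 20 pilot + 135 = 155 nor 20 + 145 = 165.
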